Pandemic-Proofing Simulation-Based Education: Development and Evaluation of Interactive Virtual Educational Content for Medical Trainees

[name], [name], [name], [name], [name]

April 15, 2023

COVID-19 Pandemic Response Funding Program

[Amended Protocol April 2023](#)

Background: During the global pandemic of 2020, simulation centres were forced to close or significantly curtail activities in an effort to reduce the spread of COVID-19. For 4 months, medical students and residents were unable to participate in simulation-based training that are core to their established curriculum. At the University of Ottawa Skills and Simulation Centre (uOSSC), this resulted in the cancellation of approximately 352 sessions with an estimated loss of 28,000 learning hours. As regions gradually reopen, significant restrictions in group sizes mean that in-person experiential learning will continue to occur at a fraction of pre-pandemic times. When combined with restricted access to clinical environments for learners, this presents an important challenge for the preparation of future and current health care workers, and thus patient safety¹. Many of the skills learned during hands-on simulation sessions are difficult to recreate through lectures or small group discussions¹. The goal of this project is to develop and evaluate virtual reality (VR) simulation modalities for their effectiveness in preparing residents to manage patients in uncertain and time-pressured conditions.

Traditional theatre-based simulation sessions require the physical presence of interdisciplinary groups of learners caring for a physical mannequin-based patient, where social distancing is challenging. However, the rapidly evolving field of virtual reality (VR) applied to healthcare education^{2,3} may provide effective physically distanced solutions should another pandemic or second wave impacts our ability to deliver face-to-face educational content. Virtual reality is defined as “*a real or simulated environment in which a perceiver experiences telepresence*”, with telepresence defined as “*the experience of presence in an environment by means of a communication medium*”.

Imagine a virtual classroom - learners wearing VR headsets in the safety of their home are immersed in a computer-generated simulation centre. Through their avatars, they can interact from a first-person perspective with their environment, colleagues and instructors. The virtual patient has been in a car accident and the learners, by interacting with the virtual trauma bay environment, must work together to perform a primary trauma survey and resuscitate the patient. The **interactive VR** environment provides the team with real time information in a realistic environment that includes the uncertainty, noise, and time pressures of a real case. At several key points in the VR video, learners are presented with interactive decision points, and their choices determine how the rest of the video unfolds

Alternatively, imagine a second immersive environment based on high-definition **360° video** obtained from our simulation centre. Single learners, wearing a VR headset, find themselves in the resuscitation room, at the foot of the bed, leading a trauma team through the assessment and resuscitation of a patient in a virtual scenario. An example of a non-interactive VR video developed by our team for the obstetrical curriculum can be found at (<https://youtu.be/AqdwMHPe0BY>).

In both the interactive VR and 360° video experiences as well as the pre- and post-test traditional theatre-based simulations, our study will aim to measure participants' heart rate (HR), heart rate variability (HRV) and oxygen saturation levels as markers of arousal and stress responses. These will serve as a physiological indication for: 1) their comfort and change in comfort when leading scenarios and making decisions for critically ill patients in real-time and 2) their emotional engagement in their own learning throughout the immersive experiences.

The properties of VR hypothesized to result in effective learning - over lectures, passive videos or discussion groups - include those of vividness (representational richness with which information is presented to the various senses) and interactivity (the ability to actively modify an environment). Increased vividness and interactivity can lead to greater emotional, motivational and cognitive engagement with learning materials. In turn, this greater engagement can lead to more active learning (analyzing, synthesizing and evaluating information rather than passively receiving it), and thus better knowledge retention and ability to apply this knowledge for subsequent problem solving. To date however, work related to VR has been targeted towards development of the technological resources to permit realistic and immersive experiences. Significant advances have led to this technology being readily affordable and accessible. However, little research has been conducted to determine the educational effectiveness of virtual simulations. Both interactive VR and 360° video provide immersive and interactive components; however, 360° video is arguably more of a passive experience for the learner. We felt that our constructed interactive VR simulation may provide more opportunity for interactivity for the learner and encourage them to participate in more active decision-making, but may increase extraneous cognitive load for the learner given the new environment. Both interactive VR and 360° video techniques require a significant investment of time and resources, but we do not yet know whether these techniques are equivalent in terms of learning or if one significantly differs from the other. There is no evidence to suggest that one method is superior to the other, therefore we chose to do a comparison study to investigate for any significant difference between these simulation experiences.

The present application is for the development and evaluation of two VR simulations (interactive VR, 360° video) applied to the context of Emergency Medicine. The aim of this pilot study is to develop two VR simulations, and to compare their effectiveness with traditional theatre-based simulations. Given the novelty of both interactive VR and 360° video simulations, our primary objective is to compare knowledge retention and application of knowledge during a paper quiz and traditional theatre-based emergency department simulations following preparation with either 360° video training or interactive VR training. The secondary objectives are to assess the usability and feasibility (resources), as well as the emotional engagement, of the above three modalities.

Methods:

Phase 1: Creation of Content: A software engineer with expertise in video-game development will be hired to develop the computer-generated emergency department in collaboration with the educators and clinicians on the team. A theatre-based trauma scenario from the current uOttawa Emergency Department curriculum will be adapted to the **VR platform**. This virtual environment will allow a team of students to manage a patient simultaneously through their avatars, from a first-person perspective. In parallel, a well-managed depiction of the same scenario will be scripted and recorded using a **360-degree HD video** camera. The recording will be made using the investigators as actors, with additional interprofessional volunteers recruited as needed. These videos will be edited and then converted to an application that can be uploaded to the Oculus® platform. Both platforms will undergo piloting for content and usability. The amount of time, money and other resources required to develop each of these scenarios will be calculated.

Phase 2: Evaluating the intervention:

Participants: 40 residents and medical students will be recruited to participate in the evaluation of the VR modules. Participants will be randomized to one of two groups (20 participants per group) – interactive VR or 360° video education. See Figure 1.

Pre-Test: Prior to participating in one of the two educational interventions (360°-video or interactive VR), participants will complete a pre-test of their content-specific knowledge and knowledge application with respect to basic presentations to the emergency department. All participants will complete a video-recorded simulation of an emergency department case, half will complete Case A while the remaining half will complete Case B. These cases will be counter-balanced at post-test in order to account for any possible differences in case difficulty. All participants will also complete a knowledge test which will consist of approximately 20 multiple-choice questions with a mark out of 20 for a minimum score of 0 and maximum score of 20. Questions will be based on Advanced Cardiac Life Support (ACLS) guidelines and algorithms. Team performance will be recorded for subsequent scoring (see measures and analysis section below). During the traditional theatre-based simulation sessions, we will measure the learners' HR and HRV with the use of a Polar H10™ chest belt linked with a commercial capture and analysis software (EliteHRV™) program on an iPad. This will allow us to measure both arousal and stress responses, as physiological indication of the learners' emotional engagement.

Intervention: Following the pre-test, participants will either participate in the interactive VR or the 360° educational video. In each condition, the scenarios will be matched for duration, and will be followed by a debriefing session focused on the learners' comprehension of the case, their rationales for decisions, as well as closing any observed gaps in performance. UOSSC-affiliated instructors with formalized simulation and debriefing training will lead the debriefing. The learners' HR and HRV will be captured during the simulation and the debriefing sessions as a measure of engagement during the activity.

Post-Test: Two weeks after the education session, all participants will complete a post-test of their knowledge and knowledge application (matched in difficulty with pre-test), as well as lead a theatre-based simulated case. Participants who completed Case A will now complete Case B and vice versa. The sessions will be videotaped for subsequent rating of clinical and team performance. We will also capture their HR and HRV again as measures of physiological arousal and stress.

Measures and Analyses:

This will be an equivalency study which hypothesizes that there will not be a difference in learning between 360-VR or interactive VR. The primary outcome measures for this study will be changes in knowledge and in clinical performance from pre-test to post-test. Two experienced simulation instructors will view and score the videos, blinded to the group allocation and whether the scenario is pre or post the intervention. The raters will evaluate the learners using the Ottawa GRS scale as well as a checklist of expected actions for the scenario. The raters will independently rate the videos, and their level of agreement will be calculated using an intra-class correlations coefficient. The averaged scores, as well as scores on the knowledge tests, will be submitted to separate mixed-design analyses of variance (ANOVA) with time (pre, post) as a repeated-measure and groups (interactive VR, 360° video) as a between-subject variable. Post-hoc analyses will be conducted with relevant paired or unpaired t-tests.

The secondary outcomes measures are arousal and stress responses during pre and post theatre-based simulation sessions, educational sessions, and debriefing sessions. Mean and peak HR and HRV (rMSSD, pNN50) will be submitted to separate ANOVAs, with time (pre-test, debriefing, post-test) as a repeated measure and group (interactive VR, 360° video, theatre-based) as a between-subject variable. Post-hoc analyses will be conducted with relevant paired/unpaired t-tests.

Another secondary outcome measure will be the cost-effectiveness of the education interventions, based on Levin’s cost effectiveness model⁴ applied to simulation-based education⁵. The cost categories will include equipment and materials (e.g. market price of equipment, maintenance cost), personnel costs (e.g. staff salary, volunteer time), facility costs (e.g. facility rental fee, facility maintenance), required client inputs (e.g. learner costs, opportunity costs), and other program costs (e.g. communications fees, servers for storage and retrieval of information). These will be summed into a dollar estimation for each modality, and compared using a one-way between-subject ANOVA, with group (interactive VR, 360° video) as the between variable.

Outcome: After six months, we will have developed interactive, virtual educational content for training medical students and residents in emergency medicine using two different VR modalities. These modalities will be easily scalable to other programs across the Faculty of Medicine. In addition, the evaluation phase will result in data to help support decisions regarding which virtual modalities are best suited to distanced simulation, in terms of educational effectiveness (knowledge, clinical performance and emotional engagement) and required costs. The calculations of costs associated with each modality will also allow for fact-based estimations of future investments in virtual-reality education.

Budget Request: \$50,000 for 1 year

Budget Justification:

Item	Price	Total
Computer Engineer	80,000/year, for 6 mos.	\$40,000
Research Assistant	5 hrs/week for 6 mos. X \$40.hr	\$7,200
Oculus Quest headset		\$800
Insta360 ONE X camera bundle with tripod		\$600
InstaVR app VR platform	\$199 USD/month = 270 CDN x 5 mos.	\$1350
		\$49,950

Computer Engineer: A software engineer, with expertise in computer-generation of environments for virtual platforms, will be hired on a full-time basis for a period of 6 months. During this period of time, the individual will work with the team to create an interactive VR trauma bay scenario (that can subsequently be adapted to other clinical content), as well as develop the 360° video based on recordings made by the team.

Research Assistant: The research assistant will support the team in the recruitment, scheduling, data collection, and data entry and analysis elements of the project. We will contract a skilled research assistant from DIME’s Research Support Unit, at their standard rate of \$40/hr

References

¹ Cook, David A., Ryan Brydges, Stanley J. Hamstra, Benjamin Zendejas, Jason H. Szostek, Amy T. Wang, Patricia J. Erwin, and Rose Hatala. "Comparative effectiveness of technology-enhanced simulation versus other instructional methods: a systematic review and meta-analysis." *Simulation in Healthcare* 7, no. 5 (2012): 308-320.

[figure not shown]
² Drummond D, Hadchouel A, Tesnière A. Serious games for health: three steps forwards. *Adv Simul (Lond)*. 2017;2:3. Published 2017 Feb 4. doi:10.1186/s41077-017-0036-3

³ Pasquier P, Gaudry S, Tesniere A, Mignon A. New insights into virtual medical education and assessment, Serious Games, and Digital Platforms. *Bull Acad Natl Med*. 2015;199(7):1153-1164.

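### Interactive VR is described as a team exercise and 360° video as a solo one, Phase 2 does not fix the session format, and the planned ANOVAs would understate the standard error if VR sessions are shared

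*Protocol*

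**What the plan says.** The Background section of the protocol sketches the two modalities. For interactive VR, "the learners, by interacting with the virtual trauma bay environment, must work together to perform a primary trauma survey". For 360° video, "Single learners, wearing a VR headset, find themselves in the resuscitation room". Methods, Phase 1 returns to the team format for the VR platform: "This virtual environment will allow a team of students to manage a patient simultaneously through their avatars, from a first-person perspective".

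Phase 2 randomises individuals: "Participants will be randomized to one of two groups (20 participants per group"), 40 in all. Its Intervention paragraph says only that "participants will either participate in the interactive VR or the 360° educational video". It matches the scenarios on duration and gives both conditions a debrief. It gives no number of learners per session or per debrief for either arm.

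Measures and Analyses specifies mixed-design ANOVAs with time (pre, post) as the repeated factor and "groups (interactive VR, 360° video) as a between-subject variable", followed by paired or unpaired t-tests. Neither team nor session appears in the model.

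**The concern.** The only format that the protocol describes for interactive VR is a team. If Phase 2 follows that description, learners randomised individually to VR would be treated in groups, while those randomised to 360° video would be treated alone. This is a partially nested design, with clustering in one arm. Learners who go through the same VR session meet the same course of events and depend on one another's decisions, so their later scores may be correlated. An ANOVA with only time and group takes its error term from learners treated as independent and does not carry that correlation.

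Two things are at stake. The first is the size of the test: an understated standard error gives too many false findings of a difference between modalities. The second is interpretation. The Background rationale contrasts the interactivity of VR with the more passive 360° video. If one arm also learns in teams and the other alone, any arm difference includes team versus solo learning, and no model term can separate the two afterwards.

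**Working it through.** **The plan's own figure.** The sample size is 40, or 20 per group. The protocol gives no alpha, power, effect size or standard deviation for it, so it cannot be reproduced. For reference only, at an assumed two-sided 5% level and 80% power, 20 independent learners per group detect (1.960 + 0.842) × √(2/20) = 0.886 SD.

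**Inputs**
- n = 20 per group: Phase 2, Participants.
- Analysis: the group-by-time test of the planned ANOVA. With two time points it equals an unpaired t-test on change scores.
- Team size m: not in the protocol; assumed 2, 4 or 5, giving 10, 5 or 4 VR teams.
- Within-team correlation ρ: not in the protocol; assumed 0.05 to 0.30. It is unrelated to the rater-agreement coefficient in Measures and Analyses.
- Clustering in the VR arm only; 360° learners independent; equal total variance in both arms.

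**Formulas**
- Design effect in the VR arm: DE = 1 + (m − 1)ρ.
- Effective VR sample size: 20/DE.
- True over planned standard error of the arm difference: √[(DE + 1)/2].
- Detectable difference with the correct error: (1.960 + 0.842) × √(DE/20 + 1/20).

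**Worked ends of the range**
- m = 2, ρ = 0.05: DE = 1.05; ratio √(2.05/2) = 1.012; effective n = 20/1.05 = 19.0.
- m = 5, ρ = 0.30: DE = 1 + 4 × 0.30 = 2.20; ratio √(3.20/2) = 1.265; effective n = 20/2.20 = 9.1.

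**Results.** Type I error is from simulation of the unpaired t-test, 20 against 20, with 100,000 replicates per row and a nominal level of 5%.

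| m | ρ | DE | Effective VR n | SE ratio | Type I error | Detectable difference (SD) |
|---|---|---|---|---|---|---|
| 2 | 0.05 | 1.05 | 19.0 | 1.012 | 5.3% | 0.897 |
| 2 | 0.10 | 1.10 | 18.2 | 1.025 | 5.6% | 0.908 |
| 2 | 0.20 | 1.20 | 16.7 | 1.049 | 6.2% | 0.929 |
| 2 | 0.30 | 1.30 | 15.4 | 1.072 | 6.9% | 0.950 |
| 4 | 0.05 | 1.15 | 17.4 | 1.037 | 5.8% | 0.919 |
| 4 | 0.10 | 1.30 | 15.4 | 1.072 | 6.8% | 0.950 |
| 4 | 0.20 | 1.60 | 12.5 | 1.140 | 8.5% | 1.010 |
| 4 | 0.30 | 1.90 | 10.5 | 1.204 | 10.7% | 1.067 |
| 5 | 0.05 | 1.20 | 16.7 | 1.049 | 6.3% | 0.929 |
| 5 | 0.10 | 1.40 | 14.3 | 1.095 | 7.5% | 0.970 |
| 5 | 0.20 | 1.80 | 11.1 | 1.183 | 9.9% | 1.048 |
| 5 | 0.30 | 2.20 | 9.1 | 1.265 | 12.5% | 1.121 |

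With ρ = 0 the ratio is 1 and the simulated type I error is 4.9% to 5.0%. The same holds with one learner per session, whatever ρ is.

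The interpretive point needs no arithmetic. The Intervention paragraph matches the arms on duration and gives each a debrief. It does not match them on whether learners work together.

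**The case against.** The case against is substantial. The Background passage is an illustration that asks the reader to imagine a classroom; it is not a procedure. Phase 1 states what the platform will permit, not how the trial will use it. The Intervention paragraph, which governs Phase 2, prescribes no teams, and Budget Justification has one singular headset line with no quantity, which fits solo use at least as well. Each participant sits the quiz and leads a case two weeks later, which may weaken any within-team correlation. All of this stands, and it is why the point is conditional. It does not remove the point, because the protocol nowhere says that VR will be delivered solo.

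It may also be said that a team term can wait for an analysis plan. The protocol, however, names the model itself, and a session identifier has to be collected when the sessions are run.

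Comparing two packages is legitimate, and teamwork may be part of the VR package. That is fair. It limits the second concern to how a result is worded and attributed.

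Three stronger readings are tempting and are not supported:
- *That the standard errors are too small as a matter of fact.* This needs shared sessions and a positive correlation, and the protocol states neither.
- *That false claims of equivalence would rise*, since the protocol calls this an equivalency study. It sets no margin and plans no confidence interval or equivalence test. Under the planned tests, equivalence could be read only from non-significance. An understated standard error produces more significant results, so that reading would become rarer.
- *That VR team-mates share an instructor and a debrief while 360° learners do not.* One description of the debrief covers both conditions, and it does not say whether debriefs are grouped.

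**Conclusion.** The point holds conditionally. The protocol describes a team format for one arm and a solo format for the other, leaves the Phase 2 format open, and fixes an analysis that is right only if learners are independent. If VR sessions are shared and team-mates' outcomes are positively correlated, the true standard error of the arm difference is about 1% to 26% larger than the planned one, and the nominal 5% type I error is about 5.3% to 12.5%. The low end (pairs, correlation 0.05) is negligible. With teams of 4 or 5 and a correlation of 0.20 or more, the excess is 14% to 26%, which matters. Team size and correlation are both assumptions, and nothing in the protocol favours one part of the range. If sessions are solo, there is no error.

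Under shared VR sessions, an arm difference could not be attributed to interactivity alone, whatever the correlation. The change is cheap and worth making before sessions are run.

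**What to change.** State in the Phase 2 Intervention paragraph how many participants share a session and a debrief in each arm. Then choose one of two routes.

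1. Run interactive VR with one participant per session, matching the solo 360° format. If debriefs are individual too, the planned ANOVA can stand on this point.
2. If VR is run in teams, record the session or team identifier for every learner, and replace the plain ANOVA with a partially nested mixed model. This has a random team effect for shared sessions, solo learners entered as singletons, and Satterthwaite or Kenward-Roger degrees of freedom. Word the conclusion as team interactive VR versus solo 360° video. If debriefs are grouped in either arm, record that grouping as well.

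The cost is a few sentences and one recorded variable, with no extra participants. Without shared sessions the model reduces to the planned analysis. The price of the second route is a wider interval, possibly clearly wider: 20 VR learners make only about 4 to 10 teams (20/5 to 20/2), so team variance is estimated on few degrees of freedom. On the assumed range, the difference detectable with 80% power rises from 0.89 SD to between 0.90 and 1.12 SD, before any further loss from those few degrees of freedom.

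### The stated aim and one secondary analysis need a theatre-trained group that the two-arm design does not contain

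*Protocol*

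**What the plan says.** The last paragraph of the protocol's Background gives three statements of purpose that do not agree.

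- The aim: "The aim of this pilot study is to develop two VR simulations, and to compare their effectiveness with traditional theatre-based simulations".
- The primary objective compares knowledge and its application "following preparation with either 360° video training or interactive VR training". Here theatre is where learners are tested, not how they are trained.
- The secondary objectives cover usability and feasibility "as well as the emotional engagement, of the above three modalities", so theatre is again counted as a modality under study.

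The design, under Phase 2 (Participants), has two arms: "Participants will be randomized to one of two groups (20 participants per group) – interactive VR or 360° video education". Under Pre-Test, "All participants will complete a video-recorded simulation of an emergency department case"; the Background makes clear that the simulations before and after training are theatre-based. Under Post-Test, each learner leads the other theatre case two weeks after the education session.

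Under Measures and Analyses, "The primary outcome measures for this study will be changes in knowledge and in clinical performance from pre-test to post-test". The primary ANOVA crosses time (two levels) with group (the two VR formats) and is followed by paired or unpaired t-tests. The ANOVA of heart rate (HR) and heart rate variability (HRV) has a between-subject group factor with three levels, the third being theatre-based. The cost ANOVA returns to two groups.

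**The concern.** An aim that names a comparator tells readers what the trial will be able to conclude. This one names theatre-based simulation, the method that the Background says was lost when simulation centres closed. Whether VR can stand in for it is the question many readers will bring. If nobody is trained by theatre, the trial cannot answer it for knowledge or clinical performance, and no later analysis plan can supply an arm that was not randomised.

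The same phantom group appears in the HR/HRV ANOVA, where it stops the planned analysis from being carried out.

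There is also a risk in interpretation. The hypothesis is that the two VR formats do not differ. Similar gains in both arms would be compatible with both formats teaching well, with neither adding anything beyond repeat testing, and with both being worse than theatre. With theatre named in the aim, and a time effect and paired t-tests in the analysis, the protocol should say which of these results may support a conclusion about modality.

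**Working it through.** **1. The plan's own figure.** Phase 2 gives 40 participants in two groups of 20: 2 × 20 = 40. This reproduces. The protocol states no alpha, power, effect size, standard deviation or margin, so there is no power calculation to reproduce.

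**2. Participants trained by theatre.** 40 − 20 (interactive VR) − 20 (360° video) = 0. Participants who have a theatre case before training: 40 of 40.

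**3. Where theatre appears, and in what role.**

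| Place in the protocol | Groups or modalities | Role of theatre |
|---|---|---|
| Background, aim | two VR formats against theatre | comparator |
| Background, primary objective | two VR formats | test setting |
| Background, secondary objectives | three modalities | modality under study |
| Phase 2, Participants | two arms of 20 | none |
| Pre-Test and Post-Test | all participants | test setting |
| Primary ANOVA | two groups | none |
| HR/HRV ANOVA | three groups | between-subject group |
| Cost ANOVA | two groups | none |

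The aim, the secondary objectives and the HR/HRV ANOVA treat theatre as something compared. The rest of the design does not.

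**4. The HR/HRV ANOVA.** A between-subject factor needs separate people in each level. The cells are 20, 20 and 0, so the third mean cannot be estimated. Filling the cell with the theatre test sessions would place the same 40 people in a VR level and in the theatre level, and the factor would no longer be between-subject.

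**5. What the primary data identify.** Let *c* be the gain common to both arms from repeat testing and the theatre pre-test, and let *v*₁ and *v*₂ be the effects of the two education packages, each with its debriefing.

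- Mean change, interactive VR: *c* + *v*₁
- Mean change, 360° video: *c* + *v*₂
- Group-by-time contrast: (*c* + *v*₁) − (*c* + *v*₂) = *v*₁ − *v*₂
- Time effect, averaged over arms: *c* + (*v*₁ + *v*₂)/2

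The common gain cancels from the randomised contrast and stays in the time effect. The effect of training by theatre appears in none of these lines.

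**6. Illustration of the time effect.** Assumptions, none of them from the protocol: outcome SD 1, pre/post correlation 0.5, two-sided alpha 0.05, no VR effect in either arm, and 20,000 simulated trials of 2 × 20. The SD of a change score is √(2 × (1 − 0.5)) = 1. The time effect was tested by a one-sample t-test on all 40 changes, and group-by-time by a two-sample t-test on the changes.

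| Common gain *c* (SD) | Time effect significant | Group-by-time significant |
|---|---|---|
| 0 | 5% | 5% |
| 0.3 | 46% | 5% |
| 0.5 | 87% | 5% |
| 0.8 | 100% (99.85%) | 5% |

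The percentages depend on the assumed gains. The pattern does not: a gain shared by both arms moves the time effect and leaves the randomised contrast alone.

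**The case against.** The strongest reply is that the trial is really a head-to-head comparison of two VR formats, and that the aim sentence is loose drafting in a self-described pilot. The primary objective, the hypothesis and the primary ANOVA all concern interactive VR against 360° video. That stands. The theatre pre-test and the quiz are common to both randomised arms, so they do not bias that contrast.

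Several stronger readings are tempting but are not supported by the document.

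- *That the protocol credits the pre-to-post gain to VR.* It nowhere says so. Change is the scale on which the two formats are compared.
- *That the Outcome section promises evidence that VR works.* It promises data to help decide which virtual modality suits distanced simulation best. That is a comparison between VR formats, and the design supports it.
- *That the debriefing and ordinary training contaminate the result.* The debriefing is described under Intervention and belongs to the education package in both arms. Ordinary training between the tests is not mentioned; the protocol gives only the two-week interval.
- *That theatre and VR cannot be compared at all.* HR and HRV are recorded in the same people during theatre and VR sessions, so engagement can be compared within person, though not by randomisation. The gap concerns knowledge and clinical performance.
- *That an untrained arm is required.* For a head-to-head question this is a design choice.

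None of this rescues the theatre comparison in the aim or the empty level in the HR/HRV ANOVA. The conflict is also more than one loose sentence, because theatre returns as a comparator in the secondary objectives and again in an analysis.

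**Conclusion.** The point holds in a limited form. The aim names a comparison with theatre that the two-arm design cannot deliver for knowledge or clinical performance: 0 of 40 participants inform it. The three-level between-subject HR/HRV ANOVA cannot be run as written. Both conclusions follow directly from the text and need no assumption.

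The randomised comparison of interactive VR with 360° video is unaffected. The time effect and paired t-tests also include repeat testing and the theatre pre-test, with no control arm to separate them from the education packages. They can describe change, but they cannot show that VR is effective in itself or comparable to theatre training. The simulated percentages rest on assumed values and only illustrate this. The protocol does not draw that inference; it should say that it will not be drawn. The matter should be corrected, because it alters what the trial may claim.

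**What to change.** All changes are to wording.

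1. **Background, aim.** State the aim as developing the two VR simulations and comparing interactive VR with 360° video, with theatre as the assessment setting.
2. **Background, secondary objectives.** Reconcile the reference to three modalities with the two-arm design: limit it to the two VR formats, or say which outcomes involve theatre and on what basis.
3. **Measures and Analyses, HR/HRV.** Make the group factor two-level (interactive VR, 360° video). If theatre and VR sessions are to be compared on engagement, define this as a within-person, non-randomised contrast between sessions. The time factor now lists pre-test, debriefing and post-test, so such a contrast would also have to include the recording from the education session.
4. **Measures and Analyses, primary.** State that conclusions about modality rest on the group-by-time contrast. State that the time effect and paired t-tests are descriptive and will not be reported as evidence that VR is effective in itself or comparable to theatre training.

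The cost is a narrower claim. The sample stays at 40 and no arm is added.

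Keeping the theatre comparison instead would need a theatre-trained arm: 3 × 20 = 60 participants, or about 13 per arm if the total stays at 40 (40/3 = 13.3). Assuming two-sided alpha 0.05 and 80% power, the detectable standardised difference between two arms is (1.96 + 0.84) × √(2/*n*). That is about 0.89 SD at *n* = 20 and about 1.10 SD at *n* = 13. Rewording is far cheaper.
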